## Study Treatment Schema

Enroll patients with recurrent high grade glioma who are planning to have craniotomy or stereotactic biopsy				
3 + 3 stage	
 
First 3 participants to a dose level will be staggered, whereby each awaits for the previous participant to have completed the 1st cycle.
 
•3+3 dose escalation/de-escalation where at least 6 pts are treated at MTD/MFDa for which <33% have DLT
 
			
Expansion Cohort	
 
8 participants to be enrolled at MTD (or MFD if MTD is not reached), all undergoing microdialysis.a
 
To determine impact of NSCs on SN-38 and irinotecan concentrations, 4 will receive first dose of NSCs at Day 15 after microdialysis, to compare with 4 who will receive first dose of NSCs on Day of Surgery.
 
			
Treatment Regimen and Assessment for Response		Immunological Studies with NSC and virus testing	Intracranial and peripheral blood SN-38 and Irinotecan concentrations	
All Patients at NSC Dose Levels 1 and -1 Procedures A-D b	Patients at NSC Dose Levels 2, 3 & 4 Procedures E-K	All Patients	First 6 enrolled, and all 8 in expansion cohort	Procedures A, C, G, I, K
Day 1: Surgery + NSCs	Day 1: Surgery + NSCs c	Pre-surgery: T cells, IgG/M, peripheral NSCs, replication competent retrovirus (RCR)	Day 1: Microdialysis catheters inserted at surgery	
Day2: Baseline MRI	Day2: Baseline MRI		Day 1: CT post-surgery to confirm catheter placement, catheter set-up	
Day3: IV Irinotecan	Day3: IV Irinotecan		Day 3-5: Microdialysis samples and blood samples pre- and post- irinotecan	
Day 17: IV Irinotecan	Day 15: NSCs via Rickham catheter	Day 15 pre-tx: T cells, IgG/M, peripheral NSCs		
	Day 17: IV Irinotecan			
Day1: IV Irinotecan	Day 1: NSCs via Rickham catheter	Day 1 pre-tx: T cells, IgG/M, peripheral NSCs, (cycle 2 only); RCR (cycle 4 & 7)	a If the maximum tolerated dose (MTD) is not reached, the maximum feasible dose (MFD) will be used.	
Day 15: IV Irinotecan	Day 15: NSCs via Rickham catheter	Day 15 pre-tx: T cells, IgG/M, peripheral NSCs	b Procedure letters are used throughout the protocol for operational guidance for the protocol user. Procedure legend is located in Tables 8.2a/b.	
	Day 17: IV Irinotecan			

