## Assigning Treatment and Correlative Study Regimen

---

A participant's starting NSC dose level, irinotecan dose schedule, correlative study procedures, and NSC regimen will be assigned by the Principal Investigator based on the following criteria:

1. Except where planned in the expansion cohort, participants who do not receive Day 1 NSCs will be replaced.
2. During the 3+3 stage of the trial, any participants who are not evaluable for dose escalation will be replaced.
3. During the 3+3 stage of the trial, the NSC dose level (-1,1,2,3, or 4) and irinotecan dose schedule (A, B, or C) will be determined using criteria defined in Section 5.3.
4. The first six patients enrolled to the trial will have microdialysis catheters inserted and undergo microdialysis and accompanying blood plasma PK studies. If one or more of the six patients does not receive cycle 1 day 3 irinotecan, the patient(s) will be replaced with the next patient(s) enrolled.
5. During the expansion cohort, all eight participants will have microdialysis catheters inserted and undergo microdialysis and accompanying blood plasma PK studies. N.B., since it is anticipated that the MTD/MFD will be 150 million NSCs (dose level 4), the 6 patients who will be treated on dose level 4 will undergo intracerebral microdialysis and be counted as part of the expansion cohort.
6. During the expansion cohort, all 8 participants will follow the NSC dose level and irinotecan dose schedule per the MTD (or if the MTD is not reached, the MFD), however 4 participants will receive their initial NSC administration on the day of surgery (Day 1), and 4 participants will receive their first NSC administration on Day 15. Participants will be grouped according to surgery type (craniotomy or biopsy). As each group enrolls participants, it will alternate between enrolling the participant to the Day 1 NSC start date and the Day 15 NSC start date. (See Section 5.4 for further explanation).

Based on the above criteria, the Principal Investigator will communicate to the clinical research team and the neurosurgeon the assigned biopsy or craniotomy procedure A-K as detailed in table 8.2a and table 8.2b.

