#### **Treatment Plan: Expansion Cohort**

---

After the MTD/MFD of the combination therapy is defined, an expansion cohort of 8 patients will be treated to gain more experience regarding the tolerability of study treatment at the MTD/MFD and to assess the biological activity of the hCE1m6-NSCs using intracerebral microdialysis. Since it is anticipated that the MTD/MFD will be 150 million NSCs (dose level 4), the 6 patients who will be treated on dose level 4 will undergo intracerebral microdialysis and be counted as part of the expansion cohort.

Four patients in the expansion cohort will undergo intracerebral microdialysis after receiving NSCs at the time of surgery followed 2 days later by IV irinotecan, but the other 4 patients in this cohort will not receive NSCs on the day of surgery. Instead they will be given IV irinotecan 2 days after surgery, and dialysate samples will be collected from them to determine how much SN-38 is present in the brain from treatment with IV irinotecan alone. These 4 patients will then receive their first dose of NSCs through the Rickham on day 15 of cycle 1 followed by irinotecan on day 17.

To determine who will receive their initial NSCs administration on the day of surgery, and who will receive their first NSC administration on Day 15 via the Rickham catheter, participants will be stratified according to surgery type (craniotomy or biopsy), and, as each group enrolls participants, it will alternate between enrolling the participant to the Day 1 NSC start date and the Day 15 NSC start date. For example, the first craniotomy participant will be assigned Day 1 NSC start date, the second craniotomy participant will be assigned Day 15 NSC start date, the third will be assigned Day 1 NSC start date, the fourth will be assigned Day 15 NSC start date, and so on as applicable. The same alternate enrollment scheme will apply to participants undergoing the biopsy procedure. The rationale for this plan is to ensure to the degree possible an even distribution of start dates for each surgery group which should increase the ability for direct comparison. There is no requirement for specific number of biopsy or craniotomy participants in the expansion cohort.

If the DLT rate in the expansion cohort exceeds 34%, the toxicity data will be reviewed.

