- hh. Imaging to be performed if the prior assessments occurred > 21 days before decision to end treatment, if patient is agreeable to have this procedure. The absence of this MRI and/or PET/CT scan with corresponding response assessment will not be considered a protocol deviation.
- ii. Response assessment using RANO criteria, at time of imaging and as indicated clinically. Dexamethasone dose to be integrated into response determination. See Section 13 for RANO criteria.
- jj. Neurosurgery will include real-time pathology review and may include Rickham Catheter and/or Microdialysis Catheter placement and/or NSC administration. See section 8.2 for details.
- kk. For participants undergoing microdialysis (procedures A, C, E, G, I, K) only, microdialysis catheter is to be removed following completion of microdialysis by the neurosurgical team. See section 8.3.6 for all relevant information.
- ll. On day of surgery, NSC administration will occur either fully during surgical procedure (craniotomy procedure A-J, biopsy procedure A-F), or will occur both during the surgical procedure **and** following the surgical procedure via the Rickham (biopsy procedures G-J only). Half of the participants in the expansion cohort will not receive Day 1 NSCs (procedure K).
- mm. Dose level 2, 3, 4 (procedures E-J) participants only. Via Rickham catheter. See Section 8.5 for procedure.
- nn. For participants undergoing Microdialysis only (procedures A, C, E, G, I, K). Post surgical non-contrast CT used to confirm appropriate placement of catheter. See section 8.3.1 for details.
- oo. For participants undergoing Microdialysis only (procedures A, C, E, G, I, K). Sampling of blood and dialysate to begin prior Day 3 irinotecan administration and up to 48 hours after irinotecan administration. For the blood pKs, a venous catheter is required. See Section 8.3.2 to 8.3.5 for details.
- pp. Irinotecan administration is detailed in Section 8.4, including required prophylaxis, observation periods and documentation for required elements
- qq. (This has been deleted)
- rr. In order to receive Day 3 irinotecan, participant must have recovered well, per the neurosurgeon (documented in clinical record), from any immediate post-operative effects, and the patient must require  $\leq$  16mg/day of dexamethasone. Otherwise the participant will be removed from all study treatments.

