- ss. Dose level 1 and -1 (procedures A-D) participants will have irinotecan administration on Day 1 and Day 15. NOTE: it is imperative that Cycle 1 is extended as needed (e.g. from 28 days to 30 days) to ensure that the Day 1 irinotecan dose occurs 14 days after the previous irinotecan dose.
- tt. Dose level 2, 3 and 4 (procedures E-J) participants only
- uu. Post-Study Treatment Medical History will consist of annual requests from the patient/patient's primary oncologist for clinical information regarding other anti-cancer therapy, progression of disease, survival, as well as information pertaining to de novo cancer, neurologic, autoimmune and hematologic disorders. In addition, unexpected medical problems including information on hospitalizations and medications will be collected. To occur annually (+/-14 days) from the start of study treatment. Alternatively, participants may come into the clinic to provide the previous year's medical history.
- vv. Efforts will be made to obtain tissue at the time of autopsy.

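### The Table 10 dosing footnotes leave procedure K (4 of the 8 expansion patients) without NSC dosing and without irinotecan from cycle 2, contradicting the Section 5 schema and Sections 5.2 and 5.4

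*Combined protocol and SAP*

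**What the plan says.** Every patient is given a procedure letter from A to K, which fixes what is done at surgery and is then used as a key elsewhere in the protocol. Letter K belongs to the delayed-start half of the expansion cohort. Table 10 footnote ll says: "Half of the participants in the expansion cohort will not receive Day 1 NSCs (procedure K").

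Table 10 then sets later dosing by letter:
- Footnote mm, NSCs on cycle 1 Day 15 and on Days 1 and 15 of later cycles: "Dose level 2, 3, 4 (procedures E-J) participants only. Via Rickham catheter".
- Footnote tt, irinotecan on Days 3 and 17 from cycle 2: "Dose level 2, 3 and 4 (procedures E-J) participants only".
- Footnote ss, the alternative irinotecan days from cycle 2: "Dose level 1 and -1 (procedures A-D) participants will have irinotecan administration on Day 1 and Day 15".

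Section 5 assigns the same treatments differently:
- The Study Treatment Schema column containing Rickham NSCs is headed "Patients at NSC Dose Levels 2, 3 & 4 Procedures E-K".
- Section 5.2 says that "all 8 participants will follow the NSC dose level and irinotecan dose schedule per the MTD" (or the MFD, if no MTD is reached).
- Section 5.4 says that the four delayed-start patients receive their "first dose of NSCs through the Rickham on day 15 of cycle 1 followed by irinotecan on day 17".

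Footnote mm sends the reader to Section 8.5. Table 8.5.2 there lists number, volume and duration of repeat NSC doses for E-F, G-H and I-J, with no entry for K.

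**The concern.** The opening of Section 8 names Section 10 and Table 10 as the place where required procedures and their timepoints are set out, so the calendar footnotes are operative dosing text. They also look deliberate: footnotes kk, nn and oo name K where it is included, and footnote ll names K to exclude it from Day 1 NSCs. A user who holds the letter K and works from the calendar finds no NSC dose and, from cycle 2, no irinotecan day. Following the cross-reference to Section 8.5 does not help.

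The expansion cohort exists partly to add tolerability experience at the MTD/MFD. The DLT section evaluates patients who have received any number of NSCs. Procedure K patients who were never given NSCs would fall outside that evaluation and would add nothing on repeat-dose toxicity or NSC immunogenicity. The likelier cost is case-by-case clarification, or recorded deviations, over intracranial dosing.

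**Working it through.** The plan states no statistical figure for this point. The check is one of coverage across procedures A to K.

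**Count.** Footnote ll puts half of the expansion cohort on K; Sections 5.2 and 5.4 say 4 of 8. 4/8 = 0.5, so the two agree.

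**NSC dosing in Table 10.** Day 1 of cycle 1 (footnote ll) covers A-J. Rickham dosing (footnote mm) covers E-J. {A-K} minus ({A-J} ∪ {E-J}) = {K}. Because footnote mm also governs cycle 1 Day 15, the gap covers every NSC dose, including those in cycle 1. In the text available to me the NSC row carries a single m. Footnote m concerns histology, so I read the marker as mm.

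**Irinotecan from cycle 2 in Table 10.** Footnote ss covers A-D and footnote tt covers E-J. {A-K} minus ({A-D} ∪ {E-J}) = {K}.

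**Irinotecan in cycle 1.** Day 3 carries only the post-operative recovery condition (footnote rr), and Day 17 carries no procedure limit. K is covered.

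**Calendar against Section 5.** Schema column {E-K} minus footnote range {E-J} = {K}. The disagreement is exactly one letter.

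| Source | NSCs via Rickham for K | Irinotecan from cycle 2 for K |
|---|---|---|
| Table 10, mm / ss / tt | excluded | in neither list |
| Table 8.5.2 | no entry | not applicable |
| Section 5 schema | included (E-K) | included (E-K) |
| Section 5.2 | MTD/MFD level, all 8 | MTD/MFD schedule, all 8 |
| Section 5.4 | from cycle 1 Day 15 | not addressed beyond cycle 1 Day 17 |
| Section 8.2, Rickham placement | reservoir placed in E-K | not applicable |

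The schema text I have shows no Day 3 irinotecan after cycle 1 for the E-K column. Table 5.3.1 gives an ongoing Day 3 and Day 17 schedule, and its only exception is dose levels 1 and -1.

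**Worst case if the calendar were followed to the letter.** Section 15.1 counts 6 + 8 = 14 patients at the MTD/MFD and states a maximum 95% margin of error of 0.27. The Clopper-Pearson half-width at 7/14 is 0.270, which reproduces it. Removing four patients leaves 14 − 4 = 10. At 5/10 the interval is 0.187 to 0.813, so the half-width is (0.813 − 0.187)/2 = 0.313.

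**The case against.** The strongest reply is that nobody reading Section 5 could doubt the plan. Day 15 Rickham NSCs for these four patients are stated in the synopsis, the design overview, the dose escalation footnotes and Section 5.4. They are given a Rickham, whose stated purpose is to deliver later NSC doses. Footnotes mm and tt open with dose levels 2 to 4, and the schema places K within those levels, so only the bracketed letters exclude K. The Principal Investigator assigns each patient's regimen (Section 5.2), explains it to the team (opening of Section 8), and settles ambiguities for the drug service (Section 14.2). This is a single-site trial.

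Most of that stands. It shows that the omission is probably a drafting slip and that patients are unlikely to miss treatment because of it. It does not make the footnotes agree with Section 5, and relying on individual clarification is a poor substitute for a correct calendar.

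A reader might draw three stronger conclusions that the documents do not support:
- **K's entries in Tables 8.2a and 8.2b are a further error.** Those tables describe surgery and day-of-surgery NSCs. K receives none that day, so not-applicable is correct there.
- **K has no irinotecan schedule anywhere.** Section 5.2 and Table 5.3.1 supply one. The gap is in the calendar, from cycle 2.
- **No repeat NSC dose exists for K.** Under Section 5.2, K follows the MTD/MFD level. If that is one of levels 2 to 4, Table 8.5.2 already has a row for it; what is missing is the link from the letter K to that row.

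**Conclusion.** The contradiction holds. Read as written, Table 10 gives procedure K no NSC dosing at any time and no irinotecan from cycle 2, while the schema and Section 5.2 put K on both and Section 5.4 starts its NSCs on cycle 1 Day 15. The size is 4 of 8 expansion patients on paper.

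A reader might infer that the trial will lose four NSC-exposed patients and that the DLT margin will widen from 0.27 to about 0.31. That is only a worst case. It needs staff to follow the calendar against Sections 5.2 and 5.4. It also takes the count of 14 as settled, whereas Sections 5.2 and 5.4 count the six anticipated level 4 patients as part of the expansion cohort. The microdialysis comparison of 4 against 4 uses the first irinotecan dose and is untouched. Correcting the text changes no sample size, power or alpha figure.

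The conclusion assumes that the calendar's NSC marker is mm. This is a correction that should be made because it concerns an operative dosing rule; it is not a flaw in the design.

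**What to change.** The sponsor should reconcile Table 10 footnotes mm and tt and Table 8.5.2 with the Section 5 schema and Sections 5.2 and 5.4, so that procedure K is assigned the same way throughout. Footnote ss should be checked in the same pass, so that every letter from A to K falls under exactly one irinotecan schedule from cycle 2. In Table 8.5.2 the link for K has to work for whichever level becomes the MTD/MFD, because the table's rows are dose levels 2, 3 and 4 and none is labelled MTD/MFD. Which assignment is right, and any number, volume, duration or day, is for the sponsor to state; none is proposed here.

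The cost is a minor amendment to two footnotes and one table. The analysis plan and sample size need no change.

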## 11 DATA AND SAFETY MONITORING, UNANTICIPATED PROBLEMS AND ADVERSE EVENT REPORTING

### **Data and Safety Monitoring**

This is a Risk Level 4 study, as defined in the “City of Hope Data and Safety Monitoring Plan”, <http://www.coh.org/dsmc/Pages/forms-and-procedures.aspx> involving gene therapy, and City of Hope holds the study’s IND.

### **Monitoring and Personnel Responsible for Monitoring**

The Protocol Management Team (PMT) consisting of the PI, collaborating investigators, CRA, protocol nurse, and statistician is responsible for monitoring the data and safety of this study, including implementation of the stopping rules for safety.

This study will use a phase I tracking log to monitor data and safety for dose escalation, recording doses administered and resultant adverse events. The tracking log will contain dose levels administered, DLT-defining adverse events, and documentation that the data from a dose level is complete before dose escalation. Those data and safety elements will be reported to the COH DSMC as applicable with the PMT report, which will be submitted quarterly from the anniversary date of activation, as noted in Table 3 below. Protocol specific data collection will include the following items: adverse events per dose level, patient outcomes, and protocol deviations.

A decision to escalate to the next dose level will be made by the PMT only after all patients on the current dose level have been observed for 4 weeks. Enrollment of the first 3 patients to a dose level will be staggered by requiring that each of the first 3 patients be separately observed for 4 weeks before the next patient can start treatment on that dose level.

Reporting of data and safety to the DSMC will occur on a quarterly basis using the PMT report until the last study patient has been observed for 4 weeks.

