### 5.1.2 Phase I Cohorts and Dose Escalation and De-escalation Criteria

Phase I Cohorts will be of 3 or 6 participants, as indicated by the dose-escalation criteria.

**Enrollment of the first 3 patients to a dose level will be staggered** by requiring that each of the first 3 patients be separately observed for 4 weeks (or until the DLT assessment period has ended) before the next patient can start treatment on that dose level.

Dose escalation will proceed through the identified doses without skipping any dose levels.

**To be counted for dose escalation**, a study patient must receive at least 80% of the assigned NSCs and 80% of the irinotecan for a particular dose level and be followed for 4 weeks OR have experienced a DLT as defined in Section 5.3.3.

All study patients enrolled are to be fully followed for toxicity; any study participant who is not evaluable for dose escalation will be replaced.

The NSC dose levels and irinotecan dose schedules are provided in Table 5.3.1. The first cohort will start at NSC dose level 1 and irinotecan schedule A.

The following dose escalation rules will be used, using the DLT definition as provided in Section 5.3.2:

- If 0/3 study participants experiences a DLT, the next cohort of 3 study patients will be treated at the next higher dose level.
- If 1/3 study participants experiences a DLT, the cohort will be expanded by another 3 study participants who will be treated at the same dose level for a total of 6 study participants.
- If 1/6 participants experiences a DLT, the next cohort of 3 study participants will be treated at the next higher dose level.
- If 2 or more participants of either a 3 participant or 6 participant cohort encounter a DLT, then the MTD has been exceeded. If applicable, three (more) participants will be enrolled at the next lower dose level.
- At least 6 patients will be treated at the MTD (or MFD, if the MTD is not reached).

If the 3+3 design rules indicate a need for de-escalation, the following will apply:

- If all DLTs in a dose level are attributed uniquely to irinotecan, then only the irinotecan schedule will de-escalate.
- If all DLTs in a dose level are attributed uniquely to NSCs, and are not attributed to 'NSCs with irinotecan', nor to irinotecan alone, then only the NSC dose level will de-escalate.

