**A DLT is defined as an adverse event that:**

- (a) is related to the administration of NSCs, irinotecan or the combination of NSCs with irinotecan, with an attribution of possible, probable, or definite, and
- (b) occurs during the first treatment cycle (including Cycle 2 Day 1 safety assessments), and
- (c) meets any of the following criteria:

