### 7.1.6 Start of Cycle Criteria

---

In order to proceed with the next cycle of study treatment:

- a) adverse events (except for alopecia) that occurred in the preceding cycle must have improved to a CTCAE v 4.0 grade  $\leq 1$  (or within 1 grade of starting values for pre-existing laboratory abnormalities),
- b) ANC must be  $\geq 1500$  cells/mm^3,

- c) platelet count  $\geq 100,000 \text{ cells/mm}^3$ , and
- d) treatment-related diarrhea has resolved.

For participants who received two administrations of NSCs with irinotecan (or irinotecan only for participants in dose level 1/1  $\geq$  cycle 2) in the previous treatment cycle, a delay of up to 14 days in starting the next cycle is allowed in order for the patient to have time to recover from toxicities of the prior cycle.

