**Table 10 Study Activity Calendar**

	Screening b	Cycle 1 a										Cycle 2+					End of Tx g	30-Day Post Tx h	Long Term Follow-Up, Autopsy i
		Day 1	Day 2	Day 3	Day 4	Day 5	Day 8	Day 10	Day 15	Day 17	Day 22	Day 1c,d	Day 3	Day 15 e	Day 17	Day 28 f			
Informed consent j	X																		
Background/medical history k	X																		
Inclusion/Exclusion criteria l	X																		
Histology confirmation	X m	X n																	
Vitals, KPS, neuro & physical exams o	X		X	X							X p			X		X	X	X q	
Adverse event assessment r	X		X	X			X			X p		X	X		X		X	X	
Concomitant meds review s	X		X	X					X p			X		X			X	X	
HLA antibody screening u	X																		
UGT1A1 polymorphism v	X																		
Immunological studies w	X x								X p			X y		X			X		
RCR testing z	X x																		
Coagulation: PT/INR, PTT	X																		
CBC with ANC aa	X			X			X		X p			X c		X c			X		
Comprehensive Metabolic Panel bb	X			X				X p			X c						X		
Serum Pregnancy Test cc	X																		
Chest X-ray and EKG	X																		
Imaging – MRI	X dd	X ee	X ff													X ff	X hh		
Imaging – PET/CT scan of the brain		X gg														X gg	X hh		
Response Assessment ii																X	X ii		
Neurosurgery		X jj			X kk														
Administration of hCE1m6 - NSCs		X ll							X m			X m		X m					
Non-contrast Brain CT		X																	
Dialysate, blood pK collection oo			X	X	X														
IV administration of irinotecan pp			X rr						X			X ss	X tt	X ss	X tt				
Post-Study Tx Medical History uu																		X	
Tissue from autopsy vv																			X

- a. For patients on dose level 1 /-1, Cycle 1 will be a minimum of 30 days to ensure that 14 days have passed between irinotecan doses.

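### Evaluability and escalation need only 4 weeks of observation, but the DLT window runs through Cycle 2 Day 1, so the next dose level can be opened before the window closes

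*Combined protocol and SAP*

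**What the plan says.** Section numbers follow the table of contents; the body prints 5.3.2 and 5.3.3 as 5.1.2 and 5.1.3, and 7.2.2 as 7.1.6.

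- **DLT window (Section 5.3.3).** Criterion (b) is that the event "occurs during the first treatment cycle (including Cycle 2 Day 1 safety assessments").
- **Evaluability (Section 5.3.2).** To count for escalation, a patient must receive at least 80% of the NSCs and of the irinotecan, and "be followed for 4 weeks OR have experienced a DLT as defined in Section 5.3.3".
- **Escalation decision (Section 11.2).** The Protocol Management Team may escalate "only after all patients on the current dose level have been observed for 4 weeks". The same section asks for a tracking-log entry that the level's data are complete, without defining complete.
- **Stagger, stated three ways.** Section 5.3.2 requires that "each of the first 3 patients be separately observed for 4 weeks (or until the DLT assessment period has ended"). Section 11.2 repeats the rule as a plain 4 weeks. The Study Treatment Schema and the Accrual Rate section require the previous patient to have finished cycle 1.
- **Cycle length.** Cycles are planned at 28 days and may be extended (Section 5.1). For dose levels 1 and -1, Table 10 footnote a says "Cycle 1 will be a minimum of 30 days". For recovery from toxicity, Section 7.2.2 says "a delay of up to 14 days in starting the next cycle is allowed".

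**The concern.** The DLT definition fixes when a patient's result is final. The two rules that use that result, evaluability and escalation, stop at a fixed 4 weeks. Only the stagger wording looks beyond 4 weeks, and it is not consistent with itself.

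A patient can therefore be counted as free of DLT, and patients can start at the next level, while by the protocol's own definition that patient may still have a DLT. This happens at the starting level on the planned schedule. The gap is longest when cycle 1 has been extended, which includes extensions to let toxicity resolve. At stake is the safety of the first patients at the next level.

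**Working it through.** **Check of the plan's own figure.** At dose levels 1 and -1 the second irinotecan dose is on Day 17, and the next must follow 14 days later: 17 + 14 = Day 31 = Cycle 2 Day 1. Cycle 1 is then 31 − 1 = 30 days, which matches Table 10.

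**Inputs.**
- Day 1 is the day of surgery (Section 5.1). The documents do not say when the 4 weeks start; I assume Day 1.
- Four weeks may end on Day 28, or on Day 29 if 28 full days must elapse. Both are shown.
- Held Day 15 NSCs may be given up to Day 22, and the cycle is lengthened to keep 14 days between NSC doses (Section 7.3).
- Held Day 17 irinotecan may be given up to Day 24, and the cycle is lengthened to keep 14 days between irinotecan doses (Section 7.3).
- Cycle 2 may start up to 14 days late (Section 7.2.2).

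**Formula.** Gap = Cycle 2 Day 1 minus the last day of the 4 weeks.

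| Case | Cycle 2 Day 1 | Gap in days (4 weeks ending Day 29 / Day 28) |
|---|---|---|
| Levels 2–4, no delay | 28 + 1 = Day 29 | 0 / 1 |
| Levels 1 and -1, planned schedule | 17 + 14 = Day 31 | 2 / 3 |
| Levels 2–4, Day 15 NSCs given on Day 22 | 22 + 14 = Day 36 | 7 / 8 |
| Levels 2–4, Day 17 irinotecan given on Day 24 | 24 + 14 − 2 = Day 36 | 7 / 8 |
| Levels 2–4, 14-day delay to cycle 2 | 29 + 14 = Day 43 | 14 / 15 |
| Levels 2–4, NSCs on Day 22 and 14-day delay | 36 + 14 = Day 50 | 21 / 22 |

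The last two rows agree with the limit in Section 7.2.1 for toxicity holds, 28 days from the last NSC dose: 15 + 28 = 43 and 22 + 28 = 50. Exceptions granted by the Principal Investigator could go further and are not counted.

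The hold and delay rows are confined to levels 2–4. The cycle 1 hold rules in Section 7.3 are written around Day 15 NSCs, and the 14-day delay in Section 7.2.2 covers levels 1 and -1 only from cycle 2 on.

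**Follow-up after a late dose.** A patient given irinotecan on Day 24 has 28 − 24 = 4 or 29 − 24 = 5 days of observation after that dose when the 4 weeks end, yet meets the follow-up condition.

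**Who is exposed.** If the stagger in the schema and the Accrual Rate section is followed, patients 1 and 2 have finished cycle 1 before patient 3 starts. The gap then falls mainly on patient 3 and, if the cohort is expanded, on patients 4–6, to whom the stagger does not apply. If the Section 11.2 stagger is followed, the next patient on the same level can also start early.

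**Sample-size figures.** The chance of seeing at least one event is 1 − 0.75^6 = 0.822 (plan: about 82%) and 1 − 0.85^14 = 0.897 (plan: about 90%). Both reproduce, and neither uses the 4-week rule.

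**The case against.** The best defence has five parts.

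1. *The 4 weeks are a floor, not a trigger.* The team may wait, and the tracking log must show complete data first. This stands as a partial safeguard. It does not settle the matter, because complete is undefined and not tied to the DLT window.
2. *The stagger already requires cycle 1 to be finished.* This holds for two of the three versions' sources, the schema and the Accrual Rate section, and it narrows the exposure as shown. It does not govern patient 3 at the escalation decision, or patients 4–6.
3. *Late DLTs are not lost.* This stands. The escalation rules and the MTD definition (Section 5.3.4) count DLTs as defined, with no 4-week cut-off, and Section 5.3.2 has every enrolled patient followed fully for toxicity.
4. *Longer holds are largely caught elsewhere.* This also stands. At levels 2–4, a patient who cannot resume by Day 22 forgoes the Day 15/17 doses and has had 1 of 2, or 50%, which is below 80%. If a related toxicity is the cause, that meets the first DLT criterion; if not, the patient is not evaluable and is replaced. The mid-cycle rows therefore concern short holds that resumed.
5. *The ordinary gap is small.* Correct: 0–1 day at levels 2–4 and 2–3 days at levels 1 and -1. Day 50 needs a full one-week hold and a full 14-day delay in the same patient.

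A reader might go further and infer that the final DLT count, the MTD or the 3+3 operating characteristics are biased. The documents do not support that. Late events still count, and no figure is given for the share of DLTs arising after week 4, so any shift in escalation probabilities would rest on an assumed share.

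**Conclusion.** The inconsistency is real and modest in size. Under the stated rules a level can be cleared with the DLT window still open: by 2–3 days at levels 1 and -1 on the planned schedule, by 0–1 day at levels 2–4 without delay, and by up to 21–22 days at levels 2–4 when a one-week NSC hold and the full start delay coincide. The consequence is that the next level may open too early. The escalation rules do not say what follows if a DLT then appears at the level below.

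This rests on counting the 4 weeks from Day 1, on the hold and delay rules as written without individual exceptions, and on the team acting as soon as the minimum is met.

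**What to change.** Reconcile the Study Treatment Schema, Sections 5.3.2, 5.3.3 and 11.2, and the Accrual Rate section to a single DLT assessment period. Use it for evaluability, stagger and the escalation decision in place of the bare 4 weeks. For example: *followed to the close of the DLT assessment period defined in 5.3.3, and in any case for no less than 4 weeks*. In Section 11.2, tie the log entry on completeness to the same period, and state the day from which the 4 weeks are counted.

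Also state when the period ends for patients who never start cycle 2. Simply requiring the Cycle 2 Day 1 assessments would leave a fully dosed patient who stops for progression or withdrawal (Section 5.5) with no end point, and would force replacement.

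The cost is a wording amendment and 0–3 days per cohort on the planned schedule, with longer waits only when cycle 1 is extended.
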